## **6. STATISTICAL CONSIDERATIONS AND ANALYSIS PLAN**

### **6.1 DETERMINATION OF SAMPLE SIZE**

A mechanistic simulation model *was* used to determine the sample size in this event-driven study, based on the following global assumptions:

- Final analysis for OS in patients with *TP53* WT disease based on two-sided log-rank test at 0.05 level of significance
- 85% power to detect an OS hazard ratio for idasanutlin + cytarabine versus cytarabine + placebo of 0.67 in patients with *TP53* WT disease, corresponding to an improvement in median OS from 6 to 9 months (50%)
- Proportion of long term survivors of 8.0% in the cytarabine + placebo arm and 16.1% in the idasanutlin + cytarabine arm

To compute the necessary number of events, we *simulated* OS times based on the following assumptions:

- All simulated OS times for patients not considered long-term survivors are exponentially distributed
- Probability of being a complete responder in the cytarabine + placebo arm is 0.16
- Probability of being a complete responder in the idasanutlin + cytarabine arm is 0.323, implying an odds ratio for CR comparing the idasanutlin + cytarabine versus the cytarabine + placebo arm of 2.5
- Probability for a complete responder to be a long-term survivor is 0.5 in either arm

- An annual dropout rate of 5% (every effort will be made to contact patients for survival information in case of study withdrawal or loss to follow-up)

To have the targeted 85% power, 275 events *in patients with TP53 WT disease* are required. The minimum detectable hazard ratio in a 2:1 randomized trial corresponding to 275 events and a significance level of 0.05 amounts to 0.78, corresponding to a minimal detectable median improvement from 6 to 7.7 months assuming exponentiality.

All patients, *regardless of TP53 mutation status*, will be randomized to this study. Assuming 85% of patients will have TP53 WT disease and 15% will have TP53 mutant disease, approximately 440 patients will be enrolled over approximately 29 months, corresponding to an estimated number of 374 patients *with TP53 WT disease*.

*In Version 6 of the protocol, an interim analysis for efficacy on OS of TP53 WT patients was added. The sample size assumptions above remain unchanged other than the recruitment time (now estimated at 41 months). The interim analysis will occur at an information fraction of 80%, providing a maximum power of 83% for the final OS analysis (see Section 6.11.2).*

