### Interim Analyses

#### Futility

A non-binding interim analysis for safety and futility will be performed by an iDMC after 120 patients with *TP53* WT have been enrolled and assessed for response. For the purposes of the *futility* interim analysis, CR is defined as confirmed CR. Sponsor personnel will not have access to by-arm efficacy and safety summaries prior to the formal reporting of study results. The iDMC may recommend stopping the study for futility if:

- the observed odds ratio for CR in the cytarabine and idasanutlin arm versus the cytarabine and placebo arm in the population of patients WT for *TP53*, is  $< 2.0$ ,
- or the observed odds ratio for CR in the cytarabine and idasanutlin arm versus the cytarabine and placebo arm in the population of patients WT for *TP53*, is  $< 2.5$  and the hazard ratio for EFS  $> 1$ .

To compute stopping probabilities for the *futility* interim analysis, the following additional assumptions are made within *TP53* WT patients and the simulation model is extended accordingly:

- Median OS for non-responders in cytarabine arm is 5.1 months
- Median OS for responders, but short-term survivors in cytarabine arm is 7.5 months
- EFS follows an exponential distribution

- Median EFS times for non-responders and CR short-term responders is assumed to be shorter by a factor 2.5 compared to OS in these same subpopulations
- The correlation between uncensored EFS and OS times is 0.5
- Hazard ratio for a comparison of idasanutlin+cytarabine versus cytarabine+placebo in both non-responders and short-term responders is 0.8

Using these assumptions, we expect 63 EFS events at the *futility* interim analysis under the alternative hypothesis. The probability of early stopping due to futility is 89.9% if the null hypothesis of equal OS survival functions is true and 31.9% if the alternative assumption of an increase in median OS from 6 to 9 months is true.

The analysis in both the *TP53* WT population and in the overall population will be provided to the iDMC.

The iDMC may recommend stopping the study for safety at the *futility* interim analysis if any of the following criteria are met (note: early death is defined as any death within the first 30 days after randomization):

- The proportion of GI toxicity (nausea, vomiting, diarrhea) events in the experimental arm (idasanutlin + cytarabine): Grade 3 >40% or Grade 4 > 15%

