## 6.11 INTERIM ANALYSES

### 6.11.1 *Futility*

A non-binding interim analysis for safety and futility will be performed by an iDMC after 120 patients with *TP53* WT have been enrolled and assessed for response. For the purposes of the *futility* interim analysis, CR is defined as confirmed CR (see definition in Section 3.4.1). Sponsor personnel will not have access to by-arm efficacy and safety summaries prior to the formal reporting of study results. The iDMC may recommend stopping the study for futility if:

- the observed odds ratio for CR in the cytarabine and idasanutlin arm versus the cytarabine and placebo arm in the population of patients WT for *TP53*, is  $< 2.0$ ,

- or the observed odds ratio for CR in the cytarabine and idasanutlin arm versus the cytarabine and placebo arm in the population of patients WT for *TP53*, is  $< 2.5$  and the hazard ratio for EFS  $> 1$ .

To compute stopping probabilities for the *futility* interim analysis, the following additional assumptions are made within *TP53* WT patients and the simulation model is extended accordingly:

- Median OS for non-responders in cytarabine arm is 5.1 months
- Median OS for responders, but short-term survivors in cytarabine arm is 7.5 months
- EFS follows an exponential distribution
- Median EFS times for non-responders and CR short-term responders is assumed to be shorter by a factor 2.5 compared to OS in these same subpopulations
- The correlation between uncensored EFS and OS times is 0.5
- Hazard ratio for a comparison of idasanutlin+cytarabine versus cytarabine +placebo in both non-responders and short-term responders is 0.8

Using these assumptions, we expect 63 EFS events at the *futility* interim analysis under the alternative hypothesis. The probability of early stopping due to futility is 89.9% if the null hypothesis of equal OS survival functions is true and 31.9% if the alternative assumption of an increase in median OS from 6 to 9 months is true.

The analysis in both the *TP53* WT population and in the overall population will be provided to the iDMC.

The iDMC may recommend stopping the study for safety at the *futility* interim analysis if any of the following criteria are met (note: early death is defined as any death within the first 30 days after randomization):

- The proportion of GI toxicity (nausea, vomiting, diarrhea) events in the experimental arm (idasanutlin + cytarabine): Grade 3  $> 40\%$  or Grade 4  $> 15\%$

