### **6.11.2**      *Efficacy*

*An interim analysis for efficacy on OS is planned to be conducted by iDMC. The efficacy interim analysis will be conducted when 80% of the OS events have occurred (i.e., approximately 220 events). At this time, it is anticipated that all patients will have been enrolled (see Section 6.1).*

*For the interim efficacy analysis of OS, the significance level will be determined using the O'Brien-Fleming alpha-spending function with overall type I error rate at 0.05 level. At the time of the interim efficacy analysis, it is expected that 80% of the OS events will have occurred, corresponding to an alpha spending of 0.025 for the interim and 0.043 for the final OS analysis leading to a power of 83% for the final analysis.*

*The iDMC will test OS for efficacy and check if there is a significant difference (alpha level 0.025 or as assessed based on actual number of OS events) in OS in favor of the experimental arm.*

*Accompanying this interim efficacy analysis, a non-binding additional futility assessment will be performed and the iDMC may recommend stopping the study for futility if the hazard ratio on OS is greater than or equal to one.*

*Further details of the interim analyses will be described in the iDMC Charter and Statistical Analysis Plan.*

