### 2.3 DETERMINATION OF SAMPLE SIZE

A mechanistic simulation model was used to determine sample size based on the following assumptions:

- Final analysis on OS in patients with *TP53* wild type (WT) using a 2-sided log-rank test at the 5% significance level
- 85% power to detect an OS HR (HR) of 0.67 for idasanutlin + cytarabine versus placebo + cytarabine in patients with *TP53* WT, corresponding to a 33% risk reduction of death, corresponding to an improvement in median OS from 6 months to 9 months (50%)
- Proportions of long-term survivors of 8.0% in the placebo + cytarabine treatment arm and 16.1% in the idasanutlin + cytarabine treatment arm

To compute the necessary number of events, OS times were simulated based on the following assumptions:

- All simulated OS times for patients not considered to be long-term survivors were exponentially distributed.
- Probability of being a CR in the placebo + cytarabine treatment arm was 0.16.
- Probability of being a CR in the idasanutlin + cytarabine treatment arm was 0.323, implying an odds ratio for CR of 2.5 for idasanutlin + cytarabine versus placebo + cytarabine.
- Probability for a CR to be a long-term survivor was 0.5 in either treatment arm.
- An annual dropout rate was 5%.

Based on these assumptions, approximately 275 OS events in patients with *TP53* WT are required to provide 85% power for the primary analysis. The minimum detectable OS HR in this study is 0.78, assuming 275 OS events and a significance level of 5%, which corresponds to a minimal detectable median improvement from 6 to 7.7 months assuming exponentiality.

All patients will be randomized in this study. Assuming 85% of patients will have *TP53* WT and 15% will have *TP53* mutant disease, approximately 440 patients will be enrolled over approximately 29 months, corresponding to an estimated number of 374 patients with *TP53* WT.

In Version 6 of the protocol, an interim analysis for efficacy on OS of *TP53* WT patients was added. The sample size assumptions above remain unchanged other than the recruitment time (now estimated as 41 months). The interim analysis will occur at an information-fraction of 80% providing a power of 83% for the final OS analysis (see section 4.11.3).

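### The 85% power is stated without saying it assumes no stopping at the CR/EFS futility analysis; with that rule followed, the plan's own 31.9% caps original design-stage power at 68.1%

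*Protocol*

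**What the plan says.** **Power.** Protocol 6.1 states "To have the targeted 85% power, 275 events" in patients with TP53 WT disease, with a two-sided log-rank test at 0.05 and a median OS of 6 versus 9 months. SAP 2.3 says that about 275 OS events "are required to provide 85% power for the primary analysis". Both synopses (the Protocol's and SAP Appendix 1) repeat the figure.

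**Version 6.** The OS efficacy interim at 80% information was added, "providing a maximum power of 83% for the final OS analysis" (Protocol 6.1). Protocol 6.11.2 gives the same figure after listing the interim and final alpha levels: "leading to a power of 83% for the final analysis".

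**Futility.** Protocol 6.11.1 says: "A non-binding interim analysis for safety and futility will be performed by an iDMC after 120 patients". The iDMC may recommend stopping if the CR odds ratio is below 2.0, or if it is below 2.5 and the EFS hazard ratio exceeds 1. Further assumptions are listed and "the simulation model is extended accordingly". The stopping probability is given as 89.9% if the null hypothesis "is true and 31.9% if the alternative assumption of an increase in median OS from 6 to 9 months is true". SAP 4.11.1 and both synopses repeat the 31.9%.

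**The concern.** The power and the stopping probability refer to the same alternative, but they appear in different sections and are never combined. The power text does not mention the CR/EFS futility analysis. It explains one reduction only, from 85% to 83%, and attributes it to the OS interim. The word maximum in Protocol 6.1 is attached to that interim, and SAP 2.3 leaves it out.

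A reader of the sample-size section therefore sees a 2-point cost for interim testing. The cost of the plan's other pre-specified stopping rule, if it is followed, is at least 16.9 points and has to be worked out from elsewhere. Power is the main justification for 275 events, so the condition it rests on should stand beside it.

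**Working it through.** **Inputs from the documents.** CR 16% (control) and 32.3% (experimental); half of complete responders are long-term survivors; 5% annual dropout; 275 events; about 374 TP53 WT patients (Protocol 6.1); 2:1 allocation (Protocol 4.2). Control median OS 5.1 months for non-responders and 7.5 months for short-term responders; HR 0.8 in both groups; stopping probability 31.9% under the alternative and 89.9% under the null (Protocol 6.11.1). Enrolment of 12 then 18 patients per month (SAP 2.4).

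**Step 1. Both figures use the same alternative.** The survival functions implied by these inputs are:

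- Control at 6 months: 0.84 × 2^(−6/5.1) + 0.08 × 2^(−6/7.5) + 0.08 = 0.372 + 0.046 + 0.080 = 0.498.
- Experimental at 9 months, with medians 5.1/0.8 = 6.375 and 7.5/0.8 = 9.375: 0.677 × 2^(−9/6.375) + 0.1615 × 2^(−9/9.375) + 0.1615 = 0.254 + 0.083 + 0.162 = 0.499.

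The medians are 5.96 and 8.97 months. The extended model used for futility is thus the 6-versus-9-month alternative used for power.

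**Step 2. Reproduce the stated figures.** Two simulations of this model (A: 40,000 trials per enrolment schedule; B: 20,000) gave:

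| Quantity | Stated | A | B |
|---|---|---|---|
| Power at 0.05, no futility stop | 85% | 85.6% | 86.1% |
| P(stop), alternative | 31.9% | 30.6% | 30.5% |
| P(stop), null | 89.9% | 89.4% | 89.3% |

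An exact binomial calculation with 80 and 40 patients gives P(OR < 2.0) = 29.6% under the alternative and 87.8% under the null, so the first branch of the rule produces most of the stopping. The 85% reproduces with futility stopping ignored.

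The 83% also comes from the alpha split alone. An O'Brien-Fleming spending function at 80% information leaves a nominal 0.0429 at the final analysis (critical value 2.025). With the drift for 85% power, 1.960 + 1.036 = 2.996, final-analysis power is Φ(2.996 − 2.025) = Φ(0.971) = 83.4%. Futility stopping does not enter.

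**Step 3. The cap.** If the rule is followed, a win requires that the trial was not stopped:

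- Upper bound: 1 − 0.319 = 0.681. This needs no simulation.
- Lower bound: 0.85 − 0.319 = 0.531.
- Smallest possible fall: 85 − 68.1 = 16.9 points.

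**Step 4. Where power lies between the bounds.** Power at 0.05 with the rule followed, planned / 41-month enrolment:

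| Version of the rule | Power |
|---|---|
| A, stopping matched to 31.9% | 61.5% / 61.3% |
| A, full rule as simulated | 62.5% / 62.4% |
| A, EFS recalibrated to the stated number of events | 62.3% / 62.2% |
| A, OR < 2.0 branch only | 63.2% / 63.0% |
| B, full rule | 62.8% / 62.6% |

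In B, (86.1 − 62.8)/30.5 = 76% of the stopped trials would otherwise have been significant, which is why the result falls below the cap.

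**Limits.** The documents expect 63 EFS events at the futility analysis; before recalibration A gave 75–78 and B about 88. Neither simulation reproduces the exact timing of that analysis, which the documents do not fully fix. Recalibrating A to 63.0 and 64.5 events moved power by about 0.2 points. The 68.1% cap depends on none of this.

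**The case against.** **The rule is non-binding.** The iDMC only may recommend, and the Sponsor decides (SAP 3.2 and 4.11). The 85% is therefore valid as power without stopping. That stands. But the rule is pre-specified and its stopping probabilities are reported as design properties, so power with the rule followed is also a design property, and it is missing. A non-binding rule does not inflate type I error, and no such claim is made here.

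**The 31.9% is disclosed.** It is printed in four places, and the cap is one subtraction away. That stands too. A reader might infer that a figure was concealed, or that the 85% or the 275 events is miscalculated. The documents support neither reading: each number reproduces for what it describes.

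**The futility analysis was past by Version 6.** Protocol 4.5.10.2 dates the decision to switch assay to September 2018, SAP Appendix 2 places the switch after the futility analysis, and SAP 4.11.1 refers to the EFS definition used at that analysis as different from the one now proposed. This limits the point. A reader might infer that the 83% drops to 68.1%, or that the continuing trial has only 68% power. Both are wrong: the 83% arrived with Version 6, when the 31.9% was no longer a future risk. The cap belongs to the original design-stage figure only.

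**The power text already refers to the final or primary analysis.** This hints at the condition but does not state it.

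**Conclusion.** The concern holds as a reporting gap of minor severity. The 85% is power with no stopping at the CR/EFS futility analysis, and none of the four places that state it says so. With the rule followed, original design-stage power is at most 68.1%, from the documents' own figure. It is about 61–63% if the mixture model is simulated under the stated assumptions, with the EFS timing caveat above. If the rule is not acted on, the 85% stands.

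Nothing follows about the validity of the 275 events, the alpha, or the power remaining once the trial had continued. Nor can a power conditional on passing the futility analysis be supplied. The documents do not say that the thresholds were met. The futility population (WT by the first assay, at least 80% of the Cycle 1 dose; SAP 4.1.1.1 and 4.11.1) also differs from the final OS population.

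**What to change.** In Protocol 6.1, SAP 2.3 and the sample-size text of both synopses, add:

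*The 85% power assumes no stopping at the non-binding CR/EFS futility analysis; at the original design stage, if that rule is followed, overall power is at most 68%.*

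Next to it, give the exact joint probability of continuing and rejecting on OS, taken from the sponsor's extended simulation model.

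In a separate sentence, say that the 83% introduced in Version 6 is power at the final OS analysis for a trial that has continued past the futility analysis, and that it does not include that earlier stopping risk. Do not set the 83% against the 68% cap.

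Events, alpha, enrolment and conduct stay as they are. The cost is a less favourable stated figure and a text amendment, which for the protocol goes through the approval route in Section 9.6.

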## **6.2 SUMMARIES OF CONDUCT OF STUDY**

Enrollment, eligibility violations, and study drug administration will be summarized by treatment arm. Patient disposition will be summarized by treatment arm and will include whether treatment was completed or discontinued early, and the reason for early treatment discontinuation.

## **6.3 SUMMARIES OF TREATMENT GROUP COMPARABILITY**

Demographic and baseline characteristics, such as age, sex, race/ethnicity, and disease status, will be summarized by treatment arm. Descriptive summaries of continuous data will present the group mean, standard deviation, median, minimum and maximum, and number of observations. Descriptive summaries of discrete data will include frequencies and percentages.

## **6.4 EFFICACY ANALYSES**

Patients will be analyzed according to the treatment arm to which they were randomized. *The TP53 WT population is the efficacy population and refers to all randomized TP53 WT patients as identified by a central laboratory test (see Section 4.5.10.2).*

*Description of efficacy analysis in this section is valid for both interim and primary analysis.*

#### **6.4.1 Primary Efficacy Endpoint**

The primary efficacy endpoint, OS, is defined as the time from randomization to death due to any cause. OS for patients who have not died at the time of the analysis will be censored at the date last known alive.

*The primary OS analysis of the study will assess the null hypothesis of equality of OS functions in the idasanutlin in combination with cytarabine (MDM2-chemo) arm versus the cytarabine given with a placebo (chemo) arm in the TP53 WT population as follows:*

H0:  $OS_{MDM2-chemo} = OS_{chemo}$  versus H1:  $OS_{MDM2-chemo} \neq OS_{chemo}$

A formal treatment comparison will be made using a two-sided stratified log-rank test at a significance level *defined using the O'Brien-Fleming alpha-spending function with overall Type I error rate at 0.05 corresponding to available information (see Section 6.11.2)*. Stratification factors that will be used are the same as for randomization, that is, age (<60 versus  $\geq 60$  years), cytogenetic and molecular risk (*favorable/intermediate versus adverse*), prior response to initial anti-leukemic therapy (refractory versus CR  $\geq 3$  months but  $\leq 1$  year versus CR > 1 year) and prior HSCT versus no prior HSCT.

Survival curves in each treatment arm will be estimated using Kaplan–Meier estimates. The Kaplan–Meier estimates will provide a visual description of the survival curves and the difference across treatment arms. The treatment effect will be quantified via a hazard ratio, computed from a stratified Cox proportional-hazards regression, including a 95% CI. To further describe and quantify OS, estimated median OS per arm and 1-year and 2-year survival probabilities, all including 95% CI, will be given. The effect of prognostic factors on OS will be assessed in an exploratory analysis using Cox multivariate regression.

#### **6.4.2 Secondary Efficacy Endpoints**

*The following secondary endpoints will be tested for the TP53 WT population, as described in the Statistical Analysis Plan:*

- CR proportion
- EFS
- ORR (CR, CRp, and CRi)
- DOR (*duration of remission following CR*)
- Proportion of HSCT *following CR*
- CR proportion and OS in clinically actionable mutation-defined subpopulation (FLT3, IDH1, and IDH2)

*Patients with no response assessments (for any reason) will be considered non-CR.*

*Difference in proportions of CR will be assessed between the two treatment arms using Cochran–Mantel–Haenszel test stratified by randomization stratification factors. In addition, proportions and 95% CI will be reported for each treatment arm. The effect of prognostic factors on CR will be assessed in an exploratory analysis using logistic regression.*

EFS is defined for all patients and measured from the date of randomization. It is measured until treatment failure, relapse from CR, or death from any cause, whichever occurs first. For patients with none of these events before *time of analysis*, EFS is censored at the date of the patient's last response assessment.

*DOR is defined for patients achieving CR and is the time from achieving CR until relapse or death from any cause, whichever occurs first. For patients with none of these events before time of analysis, DOR is censored at the date of the patient's last response assessment.*

EFS and *DOR* will in general be analyzed using the same statistical methods as those described for OS. If only very few patients qualify for *DOR* analysis, only descriptive statistics will be given.

*ORR (CR, CRp, and CRi) and proportion of HSCT will be compared between the two treatment arms using the same statistical methods as those described for CR.*

